10.3. Level of significance and power

A two-sided significance level of 5% will be applied. For information regarding the power see section 10.2.

10.4. Pass/fail criteria

The purpose of this investigation is fulfilled if the performance of the products in the two arms is comparable in terms of wound area, while the mean total cost for Biatain® Silicone is significantly lower than for Standard of Care.

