Clinical Investigation Plan

CP351 - BISIL

Biatain® Silicone 3D fit

[figure not shown]
A randomised controlled investigation comparing the clinical performance and cost effectiveness of Biatain® Silicone with standard of care dressing including filler in chronic wounds

January 2023 - January 2024

IRAS ID: 315855

Last submission date: March 15, 2023

CHANGE LOG

This confidential document is the property of Coloplast A/S. No unpublished information contained herein may be disclosed without written approval of Coloplast A/S.

SYNOPSIS OF THE CLINICAL INVESTIGATION

Title and aim

A randomised controlled investigation comparing the clinical performance and cost effectiveness of Biatain® Silicone with standard of care dressing including filler in chronic wounds.

The overall aim of this investigation is to evaluate the clinical performance and cost-effectiveness of Biatain® Silicone compared to standard of care (SoC) defined as Mepilex® Border and AQUACEL® EXTRA™ Hydrofiber® Dressing in the treatment of chronic wounds with wound depth down to 20 mm.

Investigational test product and comparator

The investigational test product is Biatain® Silicone. Biatain® Silicone is intended to be used for moist wound healing and exudate management.

The comparator products are Mepilex® Border and AQUACEL® EXTRA™ Hydrofiber® Dressing.

Intended use and purpose

All products, investigational test products as well as comparator products, are CE-marked and will be used within the intended purpose, indications and user population.

Objectives

The primary objective is to demonstrate that the clinical performance of Biatain® Silicone is comparable to standard of care (Mepilex® Border and AQUACEL® EXTRA™ Hydrofiber® Dressing).

The secondary objective is to evaluate the cost-effectiveness of Biatain® Silicone compared with standard of care (Mepilex® Border and AQUACEL® EXTRA™ Hydrofiber® Dressing).

Design of the investigation

The clinical investigation is a two-arms, open-labelled, stratified, randomized, controlled, multicentre investigation.

The cohort will in total consist of 100 subjects with chronic wounds with wound depth down to 20 mm. The subjects will be included and randomised to one of two groups receiving either Biatain® Silicone or Mepilex® Border and AQUACEL® EXTRA™ Hydrofiber® Dressing at >12 sites across the UK.

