3.1. Primary objective

The **primary objective** is to demonstrate that the clinical performance of Biatain® Silicone is comparable to standard of care (Mepilex® Border and AQUACEL® Extra Hydrofiber Dressing)

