6.3. Subject withdrawal criteria

A subject can withdraw from the investigation at any time for whatever reason without any consequences for their future treatment outside the clinical investigation. The Investigator may withdraw a subject from the investigation at any time if they judge it to be in the subject's interest.

The investigator must withdraw a subject from the investigation due to:

- Major noncompliance with the Clinical Investigation Plan (CIP) impacting the scientific integrity
 of the investigation.
- If subject's safety and wellbeing is compromised by further participation.
- Subjects lost to follow-up. At least three documented attempts of contact (phone and/or written) will be made to verify subjects lost to follow-up.

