Analysis of the primary endpoint:

The percent wound area reduction (WAR) will be analyzed by an analysis of variance with treatment and wound type (VLU and DFU) as fixed effects and wound area at baseline as covariate.

The mean WAR for each treatment group will be estimated together with the 95% confidence interval. Further, the difference in mean including a 95% confidence interval between the 2 treatments will be estimated.

Analysis of the secondary endpoint:

The secondary endpoint, total cost, will be calculated as the number of products used during the investigational period multiplied by the unit price of the product. Unit price will be extracted from Drug Tarif on the date of Last Patient Out.

This secondary endpoint will be analyzed by comparing the mean cost in the two groups assuming the cost data to be normally distributed. It will be tested on a 2-sided 5% test level if the difference in mean between the two treatments is zero. Further, the mean cost for each treatment will be estimated together with a 95% confidence interval.

Analysis of exploratory endpoints:

Percentage wound depth reduction will be analyzed by the same model as described for the primary endpoint but with wound depth at baseline as covariate.

Similarly, the two endpoints related to EQ-5D-5L (the index score and the VAS score) will be analyzed by an analysis of variance with treatment as a fixed effect and the baseline measure as covariate.

The two endpoints; responder defined as a subject reaching ≥ 30% wound area reduction within the 4-week investigation period (Yes/No) and wound healed during the investigation period (Yes/No) will be analyzed by a logistic regression model with treatment and wound type (VLU or DFU) as fixed effects and wound area at baseline as covariate.

Analysis of safety endpoints:

Adverse events will be listed and summarized, if relevant. Device deficiencies and concomitant medication will be listed.

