10.2. Sample size

The primary endpoint is the percent WAR from baseline to week 4. The sample size calculation assumes that the standard deviation of WAR in each group will be similar to what was estimated in the Biatain-Ag meta-analysis, namely SD=43%(13).

A sample size of 40 completing subjects in each arm will result in a study that is powered by 80% to get a width of a 95% confidence interval for the difference in mean WAR between the two treatments of less than +/-21%. This is based on an analysis of assumed normally distributed data.

Further, the width of the 95% confidence interval for the estimated mean WAR in each treatment group will with high probability (power of 89%) be less than +/- 15%.

The expected width of the confidence intervals based on a total of 80 subjects is deemed adequate to be able to compare the performance of the 2 treatments.

To account for lost to follow-up/dropout rate of 20%, 100 subjects are required for this study.

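### The primary objective and pass/fail rule promise to show comparable wound-area performance, but the plan gives no margin, confidence-limit rule or test to decide it, and the design only estimates the difference to about ±19 points

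*Combined protocol and SAP*

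**What the plan says.** The synopsis and section 3.1 share one primary objective: to "demonstrate that the clinical performance of Biatain® Silicone is comparable to standard of care". Section 10.4 turns this into a joint pass/fail rule, under which performance of the two arms must be such that it "is comparable in terms of wound area, while the mean total cost for Biatain® Silicone is significantly lower than for Standard of Care".

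The two halves are treated differently in section 10.1. For cost: "It will be tested on a 2-sided 5% test level if the difference in mean between the two treatments is zero". For the primary endpoint, percent WAR, the model has treatment, wound type and baseline area, each group mean is estimated, and "the difference in mean including a 95% confidence interval between the 2 treatments will be estimated". No hypothesis is attached to WAR.

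Section 10.2 sizes the study on the width of those intervals, with SD 43 and 40 completers per arm, and concludes: "The expected width of the confidence intervals based on a total of 80 subjects is deemed adequate to be able to compare the performance". Section 10.3 sets a general two-sided 5% level and refers back to 10.2 for power. Sections 6.5 and 10.1 both describe the study as exploratory.

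**The concern.** Estimating a difference with an interval is a sound design for an exploratory study. It does not by itself demonstrate comparability. That needs a statement, made in advance, of how large a deficit would still count as comparable, and a rule tying the interval to that limit. Without one, half of the rule in 10.4 cannot be evaluated as written, and whoever writes the report must decide what comparable means once the WAR result is known.

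The risk is specific. If cost comes out significantly lower, which is the hoped-for effect of replacing two products with one, an imprecise WAR result could be described as comparable and the study declared a success. The absence of a significant WAR difference might be used in that way; the plan neither says so nor rules it out.

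**Working it through.** **Inputs.** SD of percent WAR 43 in each group, 40 completers per arm, 20% dropout (all 10.2); two-sided 5% (10.3). The difference is Biatain minus standard of care, so negative values are a deficit for Biatain. The documents give no margin; every margin M below is an assumption.

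**The plan's own figures.**
- SE = 43 × √(2/40) = 9.615.
- Expected 95% half-width = t(0.975, 78) × SE = 1.991 × 9.615 = 19.1 points.
- Section 10.2 instead quotes a bound: half-width under 21 with 80% probability. P(half-width < 21) = P(χ²₇₈ < 78 × (21/19.14)²) = 89%, not 80%.
- Per arm, the expected half-width is t(0.975, 39) × 43/√40 = 13.8, and P(half-width < 15) = 81%, not the stated 89%.
- The two probabilities look transposed. That needs correcting, but it does not affect this point.
- Dropout: 80/0.8 = 100, which agrees with 10.2.

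**What the interval would show.** An observed difference of 0 gives about -19 to +19. An observed 5 points against Biatain gives -5 ± 19.1, about -24 to +14.

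**Chance of clearing a margin.** Read comparable as the lower 95% limit lying above -M. With a true difference of 0, this probability is P(T > t(0.975, 2n-2)), where T is non-central t with 2n-2 df and non-centrality M/SE.

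| Case | Half-width | M=10 | M=15 | M=20 | M=25 | M for 80% |
|---|---|---|---|---|---|---|
| 40 per arm, SD 43 | 19.1 | 18% | 34% | 54% | 73% | 27.3 |
| 50 per arm, SD 43 | 17.1 | 21% | 41% | 63% | 82% | 24.3 |
| 40 per arm, covariates remove 30% of variance | 16.0 | 23% | 45% | 69% | 87% | 22.8 |
| 50 per arm, covariates remove 30% of variance | 14.3 | 28% | 54% | 79% | 93% | 20.4 |

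The 30% variance reduction is an assumption that is not in the documents; it gives a residual SD of 43 × √0.7 = 35.98. Fifty per arm is close to a best case, because the allowance in 10.2 includes loss to follow-up: "To account for lost to follow-up/dropout rate of 20%, 100 subjects are required for this study". Section 5.1 asks withdrawn subjects to complete the termination visit, but those lost to follow-up cannot. The 24-hour rule in 6.2.1 could add a few subjects.

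**If comparable means equivalence.** The word is not directional. If the whole 95% interval had to lie within ±M, 40 per arm would give about 10% at M = 20, and 80% would need M of about 31.6.

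**If non-significance were read as comparable.** This is illustration only. A true 15-point deficit would be non-significant 66% of the time with 40 per arm, 59% with 50, and 46% with 50 plus the covariate assumption.

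**Completers per arm for 80% at SD 43, lower-limit rule.** M = 25: 48; M = 20: 74; M = 15: 130; M = 10: 292.

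**The case against.** The strongest reply is that this is an exploratory estimation study of CE-marked products. Its overall aim is to evaluate or assess performance. Means and their difference will be published with 95% intervals, and 10.2 explicitly judges the interval width adequate for comparing the treatments. The statistician is blinded until database lock (5.9). On this view the fault is one verb in the objective and one undefined word in 10.4, and neither the analysis nor the data would change.

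The description of the design is fair and stands. It does not remove the problem. An exploratory label sits badly with an objective to demonstrate something and with a section headed as pass/fail criteria. Reporting the interval leaves the verdict to be made afterwards. Blinding protects data decisions before lock but supplies no criterion. The adequacy statement in 10.2 and the general 5% level in 10.3 do not say what result would count as comparable.

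A second point also stands: a lower-limit rule is only one reading of comparable, and the cheaper one. An equivalence reading makes the gap between claim and design wider.

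**Conclusion.** The concern holds and should be fixed before any results by arm are seen. The objective and 10.4 claim something that the plan has no rule to decide. At 40 completers per arm and SD 43, the planned size would support the claim with 80% probability only if a WAR deficit of about 27 points were acceptable. Under the most favourable assumptions examined (all 50 per arm evaluable, covariates removing 30% of the variance) the figure is still about 20 points.

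These figures rest on the plan's SD, normally distributed data and a true difference of zero. The absence of a rule rests on no calculation: it follows from reading the synopsis and sections 3.1, 10.1, 10.2, 10.3 and 10.4 together.

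**What to change.** **Recommended.**
- In the synopsis and in 3.1, reword the primary objective as estimating the difference in mean percent WAR between Biatain Silicone and standard of care, with a 95% confidence interval.
- In 10.4, remove comparability as a pass/fail condition and report the WAR difference and its interval beside the cost result. The cost test in 10.1 can stay.
- State that a non-significant WAR difference will not be reported as comparability.
- Make the change before database lock and before any summary of WAR by arm, since rewording afterwards would itself look driven by the results.

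The cost is a signed amendment and a more modest claim. Section 12 requires EC notification of significant changes and says substantial ones may need prior approval; 15.1 sends every amendment to the EC. No extra patients, visits or data are needed.

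**Alternative, only if the sponsor can justify a margin that the planned size supports.**
- Define comparable in 10.4 as the lower limit of the two-sided 95% interval for Biatain minus standard of care lying above minus that margin. Say explicitly that this is non-inferiority and not equivalence.
- Fix the margin by amendment, to the same deadline.
- Name the deciding analysis set, since 10.1 runs everything on ITT and PP without ranking them, and reconcile it with the actual-product rule in 6.5.
- State the power at 80 completers, and use the same objective wording in the synopsis, 3.1 and 10.4.

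This costs no extra patients only if a margin of about 27 points can be defended (about 20 in the most favourable assumed case). Otherwise, at SD 43 without covariate gain, margins of 20, 15 or 10 points need 74, 130 or 292 completers per arm. That is 2 × 74/0.8 = 185, 2 × 130/0.8 = 325 or 2 × 292/0.8 = 730 enrolled. An equivalence rule would need about 99, 174 or 390 completers per arm for the same margins.

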10.5. Statistical reason for termination of investigation

There will be no interim analysis and therefore no reason to terminate the investigation based on statistical considerations.

10.6. Deviations from statistical design, method, or analytical procedures

Any deviations from the statistical plan will be documented in the clinical investigation report.

11. Data management

11.1. Data collection and data management

Data management and the final statistical analyses of all measurements described in this protocol are carried out by the Medical Affairs, Coloplast A/S.

Data will be collected through an electronic data capturing (EDC) system on electronic Case Report Forms (eCRF), a secure, internet-based case report form.

The data management system used in this investigation is Rave delivered by Medidata Solutions Inc. The system is designed to be compliant with the FDA requirements of 21 CFR part 11. It is a validated data management system allowing only qualified and trained personnel to enter the system. The system has full audit trail and electronic signature. The system has restricted role-based access control.

Rave EDC, current version 2022.1.1 will be used to collect all study data.

The applications Medidata eCOA and Rave Imaging will be used to collect and measure photos of the wounds. This App is used during the investigation at every site visit where the investigator or

delegated will take a photo of the wound. A trained person will afterwards be drawing the circumference of the wounds and Rave Imaging will calculate the area of the wound. If needed, the investigator will receive an iPhone with the Medidata eCOA solution installed.

The Quality-of-Life questionnaires will be handed out to the subjects and completed on paper.

This system will be used to record all subject information collected in the investigation. for secure data tracking and centralised data monitoring ("remote monitoring") done by monitors, as defined in the monitoring plan.

The principal investigator or designee must be trained in the system prior to getting access. The training is web-based and must be completed before access to the investigation is granted. Only the principal investigator, or delegate, will be authorised to enter data in the eCRF. The sponsor will be responsible for the study specific training the investigator, or designee, in completion of the eCRF.

Principal Investigator, or designee, at the clinical site will perform primary data collection directly into the eCRF or drawn from source-document (medical records) reviews. The eCRF will be completed on a continuous basis starting from the point of enrolling the subject to final follow up.

The eCRF will be completed by the investigator, or delegate, who have signed the Site Personnel Signature and Delegation List and Clinical Investigation Training Log. It will be the responsibility of the investigator to ensure that all measurements and observations are correctly noted in the eCRF.

Adverse events should be registered following the timelines described in the Adverse Event section.

When subject and investigator are required to complete different sections in the CRF, it will be specified which sections the subject will fill in and which sections the investigator will fill in. Please see the flow chart in section 7.3 for details.

In the unforeseen situation, where site cannot establish connection to the EDC system a paper CRF (pCRF) has been printed and supplied by sponsor.

The investigator will keep a separate list of the subjects' ID numbers, names and addresses in a locked room/cabinet. Only data referred to in this clinical investigation plan will be recorded in the CRFs.

11.2. Database Management, Queries and Quality Control

The monitor, using his/her personal login information shall verify all critical data points against the source documents and issue electronic queries for the authorised clinical site personnel to respond, as defined in the monitoring plan.

The Principal Investigator, using his/her personal login information shall sign each eCRF.

Electronic edit checks are described in the Data Validation Plan and will be set up to ensure data quality. A critical quality control will be performed by the sponsor's data management team and queries issued where needed.

At the end of the study a formal data review meeting will be performed before the database will be locked.

The Data Management Procedures are further described in the Data Management SOPs

11.3. Data retention

The Investigator file must be archived for a minimum period of 10 years after the final clinical investigation report has been signed.

12. Amendments to the Clinical Investigation Plan

No changes in the clinical investigation procedures shall be implemented without mutual agreement between the principal investigator and the sponsor. The agreement of the changes must be documented by signing the corresponding clinical investigation plan amendments and registered in the Change Log.

All significant changes require notification to the EC. Substantial changes may require approval from the EC prior to implementation. (Example of significant change: Changes of inclusion criteria, end points or assessment methods)

13. Deviations from the Clinical Investigation Plan

Deviations to the Clinical Investigation Plan occurs when the activities during the clinical investigation do not comply with the EC approved investigation plan.

Minor deviations are defined as those that do not increase risk, decrease benefit, or do not have a significant effect on the subject's rights, safety, or welfare; and/or on the integrity of the data. If a deviation increases risk or decreases benefit and/or has a significant effect on the subject's rights, safety, or welfare and/or has a significant effect on the integrity of the data it is defined as a major deviation and the Investigator must inform the monitor immediately, and the monitor will report and inform the Clinical Manager or designee immediately.

The investigator is not allowed to deviate from the Clinical Investigation Plan unless, under emergency circumstances or to protect the rights, safety, and welfare of the subject(s).

For the purposes of this investigation, any variance from the protocol is considered a deviation and is to be reported.

The site will complete a deviation eCRF form for all data-related deviations and all deviations that are not related to the data (for example, an untrained nurse performing study procedures) are reported by the monitor in the Site Report – Periodic Monitoring and actions are addressed to the Investigator for completion.

If any deviations to the investigation plan are detected during the monitoring visit, the Monitor shall ensure the site reports all deviations in the eCRF or on the Deviation log in the Investigator File. Additionally, the monitor must report any deviation noted during the visit in the Periodic Monitoring Report.

Monitor will align with data management in each investigation, how data management will be informed about all deviations.

The following information about the deviation will be collected:

- Site ID, Subject ID
- Deviation Date and Investigation Visit
- Date deviation was discovered
- Clear and concise description of the event
- Does the deviation affect the safety of the subject?

Corrective action taken, including the date of the corrective action. Please note corrective
action can be site was re-educated on a procedure. Ensure the corrective action is
documented.

14. Device Accountability

All access to the investigational devices, including comparators, used in the clinical investigation is controlled by storage procedures and device accountability logs as described below. The investigational devices must only be used in this clinical investigation and only according to the CIP.

Sponsor keeps a device accountability log that states the physical location of all investigational devices from shipment of investigations devices to the investigational sites until return or disposal.

The PI, or delegate, keeps records documenting the receipt, use and return and disposal of the investigational devices, which includes:

- Name of the product received
- Date of receipt.
- Identification of each investigational device (batch no./lot no)
- The expiry dates.
- Number of products received
- Number of products distributed to subjects
- The date(s) of use.
- Subject identification.
- The date on which the investigational device was returned/explanted from the subject.
- The date of return unused, expired or malfunctioning investigational products was returned to Sponsor, if applicable

15. Statement of compliance

The clinical investigation is conducted in accordance with:

- Ethical principles that have their origin in the Declaration of Helsinki, 1964, Last amended at the 59th WMA General Assembly, Brazil, October 2013.
- MDD 93/42/EEC as amended by Directive 2007/47/EC (commonly known as the Medical Device Directive).
- MDR (EU) 2017/745
- ISO 14155:2020 "Clinical Investigation of medical devices for human subjects Good clinical practices".
- The EU General Data Protection Regulation (2016/679)
- Any applicable regional or national regulations will be specified in the country specific CIP.

